Disease eligibility for partial hepatectomy will be determined according to established surgical criteria. The ideal patient for resection has a solitary hepatocellular carcinoma confined to the liver that shows no radiographic evidence of invasion of the hepatic vasculature, no evidence of portal hypertension, and well-preserved hepatic function. There is no general rule regarding tumour size for selection of patients for resection.

Two main systems are used to stage the disease:

- The American Joint Committee on Cancer (AJCC)/ Union for International Cancer Control (UICC) TNM staging for hepatocellular carcinoma. Surgeons usually consider Stage IIIB or above to be unresectable, which includes:
 - o Single / multiple tumours of any size involving a major branch of the portal vein or hepatic vein
 - o Tumours with direct invasion of adjacent organs other than the gallbladder, or with perforation of visceral peritoneum
 - o Regional lymph node metastasis
 - o Distant metastasis
- Child-Pugh classification of severity of cirrhosis – surgical resection is most safely performed in those with class A disease (scoring 5 to 6 points according to the table below), indicating normal bilirubin and well preserved liver function.

Parameters	Points assigned		
	1	2	3
Ascites	Absent	Slight	Moderate
Hepatic encephalopathy	None	Grade 1-2	Grade 3-4
Albumin	>35 g/L	28-35 g/L	<28 g/L
Bilirubin	<34.2 mmol/L	34.2-51.3 mmol/L	>51.3 mmol/L
INR	<1.7	1.7-2.3	>2.3

The nature of the study will be explained to all patients by the attending anaesthetist or a research nurse, and they will be given an information sheet to read and decide on whether to participate. All subjects will be asked to sign informed consent. The usual practice in our institution is that the patient will either be seen in an anaesthetic clinic or, if deemed healthy enough, admitted one day before surgery for preoperative assessment, and informed consent for the study will be sought at this time.

Patients will be allocated to one of two groups according to computer-generated random numbers and they will receive either sevoflurane inhalational anaesthesia (SEVO) or intravenous anaesthesia with propofol (TIVA).

Exclusion criteria:

Pre-operative factors	Intra-operative factors

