
 - Contraindication to general anaesthesia - Autoimmune / Chronic inflammatory diseases e.g. Systemic Lupus Erythematosus (SLE), Rheumatoid Arthritis (RA) etc. - Chemotherapy in the past year - Steroid therapy - Surgery for tumour removal in the past year - patients post liver transplantation 	
 - Regional Anaesthesia 
Administration of:
 
 - Nitrous oxide - Inhalational agents (with the exception of sevoflurane)

Pre-operative care

Pre-operative assessment will be performed at the preadmission clinic or at the general ward. Patients will be fasted for intake of solid food for 6 hours and clear liquids for 2 hours. Sedative premedication will not be prescribed.

Anaesthesia and intraoperative care

SEVO Group

Patients from the SEVO group will be anaesthetized according to the following protocol:

On arrival at the operation theatre, an intravenous cannula will be inserted. Standard monitoring with pulse oximeter, non-invasive blood pressure, and three-lead electrocardiogram will be applied prior to induction. Non-invasive blood pressure (NIBP) will be checked at least every 5 minutes throughout the operation. An arterial line may be inserted at the discretion of the anaesthetist before or after induction, with invasive blood pressure monitoring in lieu of NIBP if deemed necessary. Additional intravenous cannulas or central lines may also be inserted to facilitate fluid therapy, measure the central venous pressure or administer drugs, also at the discretion of the attending anaesthetist.

Anaesthesia will be induced with titrated, manual propofol injection of 1-2 mg.kg⁻¹. Remifentanil infusion will be given for analgesia at a rate of 0.1 – 0.35 mcg.kg.min⁻¹ as required, according to haemodynamic parameters. Cisatracurium 0.15 mg.kg⁻¹ or atracurium 0.5 mg.kg⁻¹ will be used for muscle relaxation. Tracheal Intubation will be performed after induction of general anaesthesia. General anaesthesia monitoring will be used. Sevoflurane at 0.5- 1 MAC, air and oxygen will be used for maintenance of general anaesthesia. Processed EEG (BISTM) will be utilized to monitor depth of anaesthesia, aiming at a BIS value of 40-60. FiO₂ will be kept between 35-50% to maintain and SaO₂ of > 95%. Further muscle relaxants can be given during the operation if required.

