In accordance with British consensus guidelines on intravenous fluid therapy for Adult Surgical Patients [22], intraoperative fluid or blood loss will be initially replaced with balanced crystalloid solution, preferably Plasmalyte A (a physiologically balanced electrolyte solution similar to extracellular fluid), for up to 20% of body volume, with additional fluid replacement with colloid or crystalloid at the discretion of the anaesthetist. Intravenous phenylephrine, ephedrine or fluid administration may also be given for management of hypotension. Intravenous anti-hypertensive agents such as beta blockers (e.g. esmolol, labetalol) and glyceryl trinitrate can be given if hypertension occurs.

Patients will receive standardized opioid analgesia of 0.1 mg.kg^{-1} intravenous morphine intra-operatively followed by patient-controlled analgesia (PCA) morphine post-operatively, as well as local anaesthesia (0.5% levobupivacaine) injected in the areas of surgical incision during wound closure for pain control.

Forced air warming blankets will be used with the aim of keeping a core temperature of 35.5-37.5 degrees Celsius.

Ondansetron 4mg IV will be given 30 minutes before end of surgery.

Sevoflurane and remifentanil infusion will be switched off at the end of the procedure. Reversal of muscle relaxation can be achieved if required with neostigmine 50 mcg.kg^{-1} IV and atropine 20 mcg.kg^{-1} IV. Patients will subsequently be transferred to the post anaesthetic care unit (PACU) for monitoring for at least 30 minutes.

TIVA Group

Patients in the TIVA group will be anaesthetized according to the following protocol:

Monitoring and other anaesthetic procedures including the management of hypertension and hypotension will be the same as SEVO group. Induction and maintenance of general anaesthesia will be conducted using total intravenous infusion of propofol. Sevoflurane will not be used, and oxygen and air would be given to provide a FiO_2 of 30-50%.

Target controlled infusion (TCI) with a modified Marsh effect site model (Fresenius Kabi) will be used for induction and maintenance of general anaesthesia and titrated to effect. The usual effect site concentration is $1.5-3 \text{ mcg.ml}^{-1}$ and BIS monitoring will also be used to produce a value of between 40-60. As with patients in the SEVO group, remifentanil will be infused at a rate of between $0.1-0.3 \text{ mcg.kg.min}^{-1}$.

Post-operative care for both groups

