In the recovery room after surgery, numerical rating pain score (NRS) will be used to assess level of pain. Patients will select a whole number (0-10 integers) that best reflects the intensity of his/her pain, in which 10 represents the maximal imaginable pain. Boluses of 2 mg intravenous morphine will be given every 5 minutes until the numerical rating scale (NRS) is less than or equal to 4/10. A patient controlled analgesia (PCA) machine will then be connected. The machine will be configured to give 1 mg of morphine whenever the patient demands with the lockout duration set to 5 minutes. No background infusion will be given and the maximum dose limit will be 0.1 mg.kg⁻¹ per hour of morphine.

On post-operative day 1, when the patient resumes a fluid diet, oral celecoxib 200 mg will be given twice daily for 3 days.

Whilst on PCA morphine, the patient's respiratory rate, oxygen saturation (SpO₂) and sedation score will be monitored every hour. Heart rate and blood pressure will be checked every 4 hours. NRS pain scores at rest and during cough/movement, cumulative PCA morphine doses, and number of PCA demands/goods delivered, and side effects (nausea, vomiting, dizziness, hypotension, desaturation) will be recorded every 4 hours. Patients will be assessed by a "pain team" every day to determine sufficiency of analgesia, as per usual practice.

Patients will be kept on PCA morphine for at least 2 days. If NRS pain scores during cough/ movement on postoperative day 2 are less than or equal to 3/10, PCA morphine will be stopped. PCA morphine will be continued if NRS is equal or greater than 4, or if the patient remains on a high PCA use. Assessment for analgesia will be conducted daily. Evaluation for complications will be required if NRS pain score is 4 or higher on postoperative day 5. The patient will be further managed at the discretion of the anaesthetist.

After PCA morphine has been withdrawn, NRS pain scores at rest and during cough/ movement, as well as the dose and frequency of rescue analgesia used will be charted once a day until discharge.

Patient data collection

Patient data collected will include: anaesthetic technique, age at the time of surgery, sex, functional classification according to the American Society of Anesthesiologists (ASA) class, severity of surgery, procedure, tumour size, and use of opioids. This data will be obtained from the anaesthetic record and the hospital electronic patient record system.

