For this current study preliminary analysis and publication of data will be conducted after 50 patients have been recruited. Recruitment will continue until **220** patients have completed the study.

Statistical analysis

Patient demographics, disease stage, and surgery and laboratory biomarker data will be compared between TIVA and SEVO groups using chi-square and *t* tests as appropriate. The Kaplan–Meier method will be used to calculate the overall survival of patients from the date of surgery to the date of death; patients alive will be censored at the follow-up closure date. A Cox proportional hazard regression model will be used to compare the hazard of the two groups by using a univariate model.

Impact of the study and concluding remarks

Thousands of patients with a cancer diagnosis undergo surgery in Hong Kong every year. If it can be shown that anaesthetic technique can impact survival after tumour resection surgery, then this will inform both clinicians and patients regarding the most suitable method of anaesthesia for their particular situation. Through biochemical analysis of blood samples taken pre, intra, and post-surgery, the mechanisms through which anaesthetic techniques may mitigate cancer recurrence after hepatectomy can be elucidated.

References:

1. *Leading Causes of Cancer Deaths*. Healthy HK, Department of Health 2014 [cited 2016 October 12th]; Available from: http://www.healthyhk.gov.hk/phisweb/en/healthy_facts/disease_burden/major_causes_death/cancers/cancers/.
2. Zhu, R.X., et al., *Epidemiology of Hepatocellular Carcinoma in the Asia-Pacific Region*. Gut and Liver, 2016. **10**(3): p. 332-339.
3. Abrams, P. and J.W. Marsh, *Current approach to hepatocellular carcinoma*. Surg Clin North Am, 2010. **90**(4): p. 803-16.
4. Divatia, J.V. and R. Ambulkar, *Anesthesia and cancer recurrence: What is the evidence?* Journal of Anaesthesiology, Clinical Pharmacology, 2014. **30**(2): p. 147-150.
5. Heaney, Á. and D.J. Buggy, *Can anaesthetic and analgesic techniques affect cancer recurrence or metastasis?* British Journal of Anaesthesia, 2012. **109**(suppl 1): p. i17-i28.
6. Grove, C.S. and G.S. Vassiliou, *Acute myeloid leukaemia: a paradigm for the clonal evolution of cancer?* Disease Models & Mechanisms, 2014. **7**(8): p. 941-951.
7. Vinay, D.S., et al., *Immune evasion in cancer: Mechanistic basis and therapeutic strategies*. Seminars in Cancer Biology, 2015. **35, Supplement**: p. S185-S198.

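### Events during surgery are listed as exclusion criteria, so randomised patients could be removed after allocation, and nothing in the plan keeps them in their allocated arm

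*Combined protocol and SAP*

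**What the plan says.** The exclusion criteria under Research Plan and Methodology form a two-column table. One column holds pre-operative factors. The other, headed "Intra-operative factors", lists regional anaesthesia and the administration of nitrous oxide or "Inhalational agents (with the exception of sevoflurane").

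On allocation, the same section says: "Patients will be allocated to one of two groups according to computer-generated random numbers". It does not say when this happens. The arm descriptions differ from the start of anaesthesia. In the SEVO Group, "Anaesthesia will be induced with titrated, manual propofol injection"; in the TIVA Group, "Induction and maintenance of general anaesthesia will be conducted using total intravenous infusion of propofol", by target-controlled infusion. The TIVA Group section adds: "Sevoflurane will not be used, and oxygen and air would be given".

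The Statistical analysis section compares the TIVA and SEVO groups and censors patients alive at the close of follow-up. It defines no analysis population, makes no as-randomised or intention-to-treat statement, and gives no rule for a patient who meets an intra-operative criterion. The text just before it sets recruitment to run until 220 "patients have completed the study".

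**The concern.** An exclusion criterion normally decides who enters a trial, before randomisation. These items describe what happens in theatre. A patient who meets one has already been allocated, and the person whose action triggers the exclusion knows the allocation. If such patients are removed more often from one arm and differ from the rest in prognosis, the HIF-1, recurrence and survival comparisons are no longer between the groups formed by randomisation.

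The list is also uneven. Sevoflurane given to a TIVA patient is the departure that most directly erodes the contrast between arms, and the TIVA protocol rules it out, yet it is not an exclusion. Another volatile agent given to the same patient is. No section says in which arm a TIVA patient who received sevoflurane is analysed.

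**Working it through.** **Order of events.**

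1. Consent is sought in the anaesthetic clinic or at admission the day before surgery.
2. The time of allocation is not stated, but it must precede induction because induction differs by arm.
3. Nitrous oxide, another volatile agent or an unplanned regional technique comes later. A regional technique already planned at assessment is the only listed item that could be screened out before allocation.

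**Inputs from the Primary outcome and Sample size calculation sections.** Two-year recurrence 40% (SEVO) and 20% (TIVA), alpha 0.05, power 0.9, 108 per group, 216 in total, raised to 220 (110 per arm).

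**The plan's own figure.** The two-sided arcsine formula gives 108 per group and the pooled normal formula gives 109. The stated 108 is therefore reproduced with a two-sided 5% test, which is used below.

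**Illustration of bias (assumptions, not plan figures).** There is no true effect, recurrence is 40% in both arms, and a fraction q of one arm is removed. Those removed have recurrence risk r. The remaining patients in that arm have recurrence

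p = (0.40 − q·r)/(1 − q).

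The chance that a pooled z test favours that arm is

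Φ[(0.40 − p − 1.96·s₀)/s₁],

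where s₀ is the pooled and s₁ the unpooled standard error, with 110(1 − q) and 110 patients.

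Example, q = 0.10 and r = 0.8:

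- p = (0.40 − 0.08)/0.90 = 0.356, with 99 versus 110 patients
- s₀ = 0.0672 and s₁ = 0.0671
- (0.0444 − 1.96 × 0.0672)/0.0671 = −1.30, so the probability is about 9.7%

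| Removed from one arm (q) | Risk in those removed (r) | Recurrence left in that arm | Fall (points) | False positive in its favour |
|---|---|---|---|---|
| any of these | 0.4 | 40.0% | 0 | 2.5% |
| 2% | 0.6 | 39.6% | 0.4 | 2.9% |
| 2% | 0.8 | 39.2% | 0.8 | 3.3% |
| 5% | 0.6 | 38.9% | 1.1 | 3.6% |
| 5% | 0.8 | 37.9% | 2.1 | 5.0% |
| 10% | 0.6 | 37.8% | 2.2 | 5.1% |
| 10% | 0.8 | 35.6% | 4.4 | 9.7% |
| 10% | 1.0 | 33.3% | 6.7 | 16.7% |

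Exact binomial enumeration of the same test agrees to within about 0.3 points (17.0% in the last row).

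Removal from both arms:

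- 10% of one arm and 5% of the other: 3.7% (r = 0.6) or 5.3% (r = 0.8)
- 5% of each arm: 2.5%, no bias

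**Cost of keeping everyone.** Suppose a fraction q of TIVA patients is off protocol and takes on the full 40% risk, an upper bound on dilution. TIVA recurrence becomes 0.20(1 − q) + 0.40q, against 40% in SEVO with 110 per arm.

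| q | TIVA recurrence | Power |
|---|---|---|
| 0 | 20.0% | 90.5% |
| 2% | 20.4% | 89.1% |
| 5% | 21.0% | 87.0% |
| 10% | 22.0% | 82.8% |

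**The case against.** The list may have been meant as prohibited co-treatments. Both arm protocols use only air and oxygen with the allocated agent, pain control is by morphine and wound infiltration, and the background section explains why nitrous oxide and regional anaesthesia might confound the biomarkers. No sentence says that an affected patient is dropped from follow-up or analysis. The groups are defined by allocation, so comparing the TIVA and SEVO groups can fairly be read as a comparison by allocated group. The completion wording is a recruitment target, not an analysis set.

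The listed items also lie outside both protocols, and the documents give no reason why they should occur more often in one arm or in patients with a worse prognosis. Bias needs both. The illustration supplies them by assumption, and it covers recurrence, a secondary outcome, but not HIF-1.

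Much of this stands: removal from analysis is not spelled out, the time of randomisation is inferred, and the size is unknown. It does not dispose of the point. The heading over the list is exclusion criteria, and someone following it would exclude the patient. Defining groups by allocation does not say what happens to a patient who is then excluded. If co-treatment restrictions were intended, the same wording change expresses that intention.

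**Conclusion.** The concern holds as a conditional one. The plan contains a rule that, followed literally, removes patients after randomisation on the basis of events that the unblinded anaesthetist controls, and nothing in it retains them.

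Its effect cannot be estimated from the documents. Under the one-arm assumptions above, with 60–80% risk among those removed, the false-positive rate in one direction is 2.9–9.7% instead of 2.5%. The 16.7% case requires all 11 of 11 removed patients to recur and is an extreme. If removals are balanced or unrelated to prognosis, the bias is negligible. The effect on HIF-1 was not quantified.

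Confidence is medium, because the timing of randomisation and the intent of the list are inferred. The change should be made because the risk is avoidable at almost no cost.

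**What to change.** 1. Move the intra-operative items out of the exclusion criteria and record them as protocol deviations. A technique already planned when eligibility is checked can be listed as a pre-operative criterion, assessed before randomisation.
2. State when randomisation takes place.
3. State in Statistical analysis that every randomised patient is followed and analysed in the allocated arm for HIF-1, recurrence and survival, including TIVA patients who receive sevoflurane or any other volatile agent.
4. Allow a per-protocol analysis as a sensitivity analysis only.

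This changes wording, not anaesthetic care. The data are already gathered from the anaesthetic record: "Patient data collected will include: anaesthetic technique". The cost is some dilution of the contrast between arms, bounded by the power figures in the second table.

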The aim is to investigate the effect of sevoflurane inhalational versus propofol intravenous anaesthesia on expression of hypoxia-inducible factor 1 (HIF-1), circulating tumour cells, DNA damage and biomarkers of immunity and inflammation in patients with hepatocellular carcinoma undergoing open hepatectomy.

Aim 1: To investigate the changes in gene expression and plasma concentrations of inflammatory biomarkers (HIF-1, IL-6, and TNF-alpha) induced by surgery and the effects of different methods of anaesthesia on this expression.

Aim 2: To investigate the changes in DNA damage induced by surgery and the effects of these two different methods of anaesthesia on this damage.

Aim 3: To investigate changes in circulating tumour cells pre, intra and post-surgery

Aim 4: To follow-up patients post tumour resection for three-year survival and investigate differences in survival between the TIVA and sevoflurane cohorts.

Aim 5: To investigate the difference in post-operative pain and post-operative morphine consumption in patients anaesthetized with propofol versus sevoflurane.

Background of Research

Cancer remains a leading cause of morbidity and mortality, despite continued advances in management and treatment strategies. In 2014, 'malignant neoplasms' was the leading cause of death for both sexes in Hong Kong, accounting for 30.2% of all registered deaths [1]. Of these, liver cancer, defined as malignant neoplasm of the liver and intrahepatic ducts, has been the third leading cause of cancer death in Hong Kong for many years. In 2014, 1,585 patients died from liver cancer, accounting for 11.5% of all cancer deaths [2]. In general, the age-standardized death rate due to liver cancer was higher in males than females, with a decreasing trend in age-standardized death rates in recent years [2]. With the ageing population and the rising incidence of cancer diagnoses, anaesthesiologists are frequently managing patients with cancer in their daily practice.

[figure not shown]

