- Opioids are frequently used in the treatment of oncology patients, both in intraoperative and postoperative settings. Both acute and chronic opioid therapies have been shown to have immunomodulating effects. Conflicting results have been published, with opioids shown to promote and inhibit cancer metastasis in different studies.
Opioids inhibit cellular and humoral immune function in humans. They suppress NK cell activity, phagocyte function, as well as cytokine and antibody production. Opioids have been shown to increase angiogenesis and promote breast tumour growth in rat models. However, opioids may also reduce the stress response to perioperative pain, protecting against stress-induced reduction in immunity.
- Regional Anaesthesia. Intense research has been focused in this area, with multiple small studies comparing the effects of general and regional anaesthesia on cancer recurrence with variable outcomes. One postulated mechanism is that RA lowers plasma levels of cortisol and catecholamines during surgical trauma, reducing the immunosuppression caused by surgical stimulation.

In summary, cancer and in particular hepatocellular cell carcinoma is a leading cause of death in Hong Kong. Though surgical resection can be a potentially curative treatment option, patients are still largely susceptible to cancer recurrence and metastasis. There is growing interest in the factors that affect this susceptibility, particularly in the perioperative period – factors including anaesthetic techniques. Can anaesthesiology affect cancer oncological outcomes? The scientific literature cannot yet offer a definite strategy for optimal anaesthetic management in cancer patients. However, the search for the ‘anti-cancer anaesthetic’ continues, with a need for large, carefully controlled,

prospective trials to attest causation. Though any benefit of one particular anaesthetic technique over another in terms of cancer recurrence is likely to be small, nonetheless, when scaling up to incorporate the growing numbers of patients undergoing cancer surgery, even fairly simple changes in technique could save many lives.

Research Plan and Methodology

All patients aged 18-80 years old with primary hepatocellular carcinoma presenting for elective open hepatectomy surgery in Queen Mary Hospital, Hong Kong, will be invited to join this randomised, controlled trial.

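### The TIVA section likens its remifentanil infusion to the SEVO arm's but gives a different upper limit (0.3 against 0.35 mcg/kg/min), with no reason stated

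*Combined protocol and SAP*

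**What the plan says.** The SEVO Group section, under Anaesthesia and intraoperative care, states: "Remifentanil infusion will be given for analgesia at a rate of 0.1 – 0.35 mcg.kg.min⁻¹ as required, according to haemodynamic parameters".

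The TIVA Group section says of care outside the anaesthetic itself: "Monitoring and other anaesthetic procedures including the management of hypertension and hypotension will be the same as SEVO group". It then turns to remifentanil with "As with patients in the SEVO group, remifentanil will be infused at a rate of between" and gives limits of 0.1 and 0.3 in the same units, which I read in both places as mcg per kg per minute.

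The opioid paragraph in Background of Research says "Both acute and chronic opioid therapies have been shown to have immunomodulating effects" and, of their effect on immune function, "They suppress NK cell activity, phagocyte function, as well as cytokine and antibody production". The same paragraph also says that published results conflict, and that opioids may protect immunity by damping the stress response to pain.

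Aim 1 and Table 1 include IL-6 and TNF-alpha. Aim 5 is "To investigate the difference in post-operative pain and post-operative morphine consumption" between the two anaesthetics. Patient data collection lists opioid use among the items taken from the anaesthetic and hospital records. Statistical analysis names chi-square tests, t tests, Kaplan–Meier and a univariate Cox model. It does not mention intra-operative opioid dose.

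**The concern.** The trial is meant to compare sevoflurane with propofol while other care is held the same. The protocol works towards that: it excludes regional anaesthesia and nitrous oxide, fixes intra-operative morphine by body weight, and uses one recovery and PCA regimen for both arms. A remifentanil ceiling that depends on the arm runs against this intent, and the wording around it suggests that nobody meant it to differ.

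At stake is a possible difference in opioid exposure created by the protocol text rather than by the anaesthetic. It could arise only in patients who need the highest infusion rates. By the protocol's own account opioids may act on immune markers, so the plan gives a reader grounds to ask whether a difference in cytokines reflects the anaesthetic alone. As written, the plan offers no comparison that would answer that question.

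**Working it through.** The plan states no derived figure to reproduce. The check sets the two ranges side by side and does simple arithmetic on the limits.

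| Item | SEVO Group section | TIVA Group section |
|---|---|---|
| Lower limit (mcg/kg/min) | 0.1 | 0.1 |
| Upper limit (mcg/kg/min) | 0.35 | 0.3 |
| Width of range | 0.35 − 0.10 = 0.25 | 0.30 − 0.10 = 0.20 |
| Link to the other arm | none | likened to SEVO, after a statement that other procedures are the same |
| Reason for a difference | none | none |

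1. Gap in the upper limits: 0.35 − 0.30 = 0.05 mcg/kg/min.
2. SEVO ceiling relative to TIVA: 0.35/0.30 = 1.167, or 16.7% higher. Equivalently, the TIVA ceiling is 0.05/0.35 = 14.3% below the SEVO ceiling.
3. Bound on the dose difference. The documents give neither body weight nor infusion time, so this step rests on assumptions: 60 to 70 kg, and 3 to 6 hours with both arms held at their ceiling throughout. The formula is 0.05 × weight × minutes.
   - 60 kg, 3 hours: 0.05 × 60 × 180 = 540 mcg.
   - 70 kg, 6 hours: 0.05 × 70 × 360 = 1,260 mcg.
   - No patient needing more than 0.3: the unequal limits contribute 0 mcg.

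Under those assumptions, the part of any difference that the unequal limits can create runs from zero to between 540 and 1,260 mcg per patient. The upper figures are worst cases, not expectations. Where in the range the trial would fall depends on how often the rate goes above 0.3, which the documents do not say.

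4. Handling in the analysis. Opioid use is collected, but the plan does not say that total remifentanil dose is extracted, compared or reported.

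**The case against.** The strongest reply is that the opening words of the TIVA sentence may mean only that these patients also receive remifentanil, not that they receive it at the same rate. That reading is possible. It is the less natural one, given the nearby statement that other procedures match. It also leaves the arms with different opioid limits and no reason given, so the text needs attention either way.

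The second reply is that the figures bound a titrated infusion and do not assign a dose. This stands. Remifentanil use may differ between arms even under identical limits, because patients may need different amounts with different anaesthetics. Equal limits would remove only the difference that the protocol itself makes.

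Three stronger conclusions are tempting, and the documents do not support them.

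- A reader might infer that the analysis cannot separate opioid exposure from the anaesthetic. Opioid use is collected, so an imbalance could at least be described. What can be said is that no planned analysis examines it.
- A reader might infer that the higher SEVO ceiling biases the trial towards propofol. The protocol reports opioid effects in both directions, so no direction follows.
- A reader might infer a threat to the primary outcome. The opioid paragraph makes no direct link to HIF-1, and the document does not say that intra-operative remifentanil rate alters later morphine use. The relevance to Aim 5 is plausible but assumed.

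**Conclusion.** The point holds as a minor internal inconsistency. The TIVA section likens its remifentanil infusion to the SEVO arm's and says that other care is the same, yet its upper limit is 0.3 where the SEVO section has 0.35 mcg/kg/min. The documented size is that ratio, about 17%. The resulting difference in exposure is unknown and may be nil.

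The conclusion rests on reading the TIVA wording as implying the same rate, and on the absence of any explanation elsewhere in the document. Its relevance rests on the protocol's own description of opioids as immunomodulating and on its choice of cytokines, pain and morphine use as outcomes. It looks more like a drafting slip than a chosen feature of the design. It is not evidence that the arms will receive different opioid doses or that any result will be biased.

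**What to change.** Reconcile the remifentanil sentences in the SEVO Group and TIVA Group sections. Either both give the same limits, as the TIVA wording implies, or the TIVA section states that the difference is intended and why. The clinical team decides which; no dose is proposed here, and it does not follow from the documents that one range must apply to both arms.

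Add total intra-operative remifentanil by arm to a descriptive table, taken from the anaesthetic record. Patient data collection should name this dose explicitly, since it now refers only to opioid use in general. Do not enter the dose in a model as if it were a baseline covariate. It is set after randomisation and may itself respond to the allocated anaesthetic, so adjusting for it could distort the comparison between arms.

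The cost is one line in the treatment text, one named data item and one table row. Design, sample size and analysis methods are unchanged.
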